9.7 Electrocardiogram (12-Lead ECG)

Measured values and changes from baseline in heart rate, PR, QRS, QT, QTc (QT interval as correlated by Bazett's formula [QTcB] and QT interval as correlated by Fridericia's formula [QTcF]), and RR intervals at each timepoint will be summarized for the overall population and by treatment group using descriptive statistics. Criteria for potentially clinically significant ECG abnormalities in heart rate, PR, QRS, QT, QTcB, and QTcF intervals will be set (Table 16.1-2), and the number and percentage of subjects who meet the criteria will be provided for the overall population and by treatment group.

10 Efficacy Analyses

Efficacy analyses will be performed in the efficacy set.

10.1 Secondary Endpoints

10.1.1 IGA

- Incidence of success in IGA

Incidence of success in IGA at each timepoint will be compared between the 1% OPA-15406 group and the vehicle group, and between the 0.3% OPA-15406 group and the vehicle group, and p-value will be calculated, using the Cochran-Mantel-Haenszel test stratified by baseline IGA (mild or moderate). The difference in incidence of success in IGA between each OPA-15406 group and the vehicle group and its two-sided 95% confidence interval (a Mantel-Haenszel estimator of the common risk difference and its two-sided 95% confidence interval) will be computed. Additionally, two-sided 95% confidence interval for the incidence of success in IGA in each treatment group will also be calculated using Clopper-Pearson method.

The analyses will be applied to the 3 assessments defined in “[Section 6.3.1 Response in Investigator’s Global Assessment](#), 2) Sensitivity Analyses.”

The SAS code to compare the incidence of success in IGA by the Cochran-Mantel-Haenszel test and to calculate the difference in incidence of success in IGA and its two-sided 95% confidence interval is shown below.

```
proc freq ;  
  tables BaselineIGA*Treatment*Response/riskdiff(common) cmh;  
run;
```

- Change from baseline in IGA

Based on the OC data set, the change from baseline in IGA (at Week 1, Week 2, and Week 4; if the timing of discontinuation falls within the allowable window of a timepoint, the data at discontinuation will be included as the data for the timepoint) will be analyzed using the mixed model repeated measures (MMRM) analysis with treatment (0.3% or 1% OPA-15406 group, and vehicle group), timepoint, and interaction between treatment and timepoint as factors and baseline IGA as a covariate. An unstructured covariance matrix will be used to model the within-subject errors and Kenward-Roger

method will be used to calculate the standard error of fixed-effects and the degree of freedom. If the MMRM procedure fails to converge under unstructured covariance structure, the following structure will be used in the order of 1) heterogeneous toeplitz, 2) heterogeneous autoregressive of order 1, 3) heterogeneous compound symmetry and the first (co)variance structure converging to the best fit will be used. The least square mean of each treatment group will be calculated by timepoint. The difference in the least square mean between the vehicle group and each OPA-15406 group, and the two-sided 95% confidence interval and p-value will also be calculated at Week 1, Week 2, and Week 4. The least square mean and the standard error will be plotted by timepoint for each treatment group.

The SAS code to conduct the MMRM analysis is shown below.

```
proc mixed method = reml;  
class Treatment Visit Subject;  
model Change = Treatment Visit Treatment*Visit Baseline/s ddfm = kr;  
repeated Visit/type = un sub = Subject;  
lsmeans Treatment*Visit/pdiff cl alpha = 0.05;  
run;
```

“Baseline” represents the IGA at baseline.

The SAS code to use when the MMRM procedure fails to converge under the unstructured covariance structure is shown below. (Designate *type = TOEPH* for heterogeneous toeplitz, *type = ARH(1)* for heterogeneous autoregressive of order 1, and *type = CSH* for heterogeneous compound symmetry).

```
proc mixed method = reml empirical;  
class Treatment Visit Subject;  
model Change = Treatment Visit Treatment*Visit Baseline/s ;  
repeated Visit/type= TOEPH sub = Subject;  
lsmeans Treatment*Visit/pdiff cl alpha = 0.05;  
run;
```

Based on the OC and LOCF data sets, analysis of covariance (ANCOVA) model with treatment (0.3% or 1% OPA-15406 group, and vehicle group) as a factor and baseline IGA as a covariate will be applied to the change from baseline up to each timepoint. The least square mean of each treatment group will be calculated by timepoint. The difference in the least square mean between the vehicle group and each OPA-15406 group, and the two-sided 95% confidence interval and p-value will also be calculated at Week 1, Week 2, and Week 4. Based on the OC and LOCF data sets, measured values and changes from baseline in IGA at Week 1, Week 2, and Week 4 will be summarized by treatment group using descriptive statistics.

Shift tables will be created for the change from baseline in IGA (-3, -2, -1, ±0, +1, +2) at Week 1, Week 2, and Week 4.

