### 3.7.4 Efficacy Assessments

#### 3.7.4.1 Investigator's Global Assessment (IGA)

The investigator or subinvestigator will assess the skin symptoms using IGA. The investigator or subinvestigator will score the severity (0 = clear, 1 = almost clear, 2 = mild, 3 = moderate, 4 = severe/very severe) of the overall symptoms of the treatment area (erythema, infiltration, papules, effusion, and scab formation). The result will be recorded in the source document and CRF. The same subject will be evaluated by the same physician, as much as possible.

Symptom	Severity score
No inflammatory signs of AD	0 = Clear
Just perceptible erythema and just perceptible papulation/infiltration	1 = Almost clear
Mild erythema and mild papulation/infiltration	2 = Mild

Symptom	Severity score
Moderate erythema and moderate papulation/infiltration	3 = Moderate
Severe erythema and severe papulation/infiltration with oozing/crusting	4 = Severe/very severe

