6.3 Data Conversion and Calculation

6.3.1 Response in Investigator's Global Assessment

Responders and non-responders in investigator's global assessment (IGA) are defined as follows:

- 1) Primary analysis for incidence of success in IGA
 - Subjects with an IGA score of 0 (clear) or 1 (almost clear) with an improvement by at least 2 grades from baseline are defined as responders. Subjects with missing IGA data at the time of evaluation will be handled as non-responders.

- 2) Sensitivity analysis
 - Subjects with an IGA score of 0 (clear) or 1 (almost clear) with an improvement by at least 2 grades from baseline are defined as responders. For subjects with missing IGA data at the time of evaluation, the last observation carried forward (LOCF) will be used.
 - Subjects with an IGA score of 0 (clear) or 1 (almost clear) with an improvement by at least 2 grades from baseline are defined as responders. Observed cases (OC) will be used.

- Subjects with an improvement in IGA score to 0 (clear) or 1 (almost clear) are defined as responders. Subjects with missing IGA data at the time of evaluation will be handled as non-responders.

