6.6 Significance Level and Confidence Coefficient

No significance tests will be used in this trial; therefore, no significance levels are set. The confidence coefficient is set at two-sided 95%.

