10.4 Subgroup Analysis

Incidence of success in IGA will also be analyzed in the following subgroups in the same manner as described in [Section 10.1.1](#).

Age: <7 or ≥7 years old

Gender: Male or female

Baseline IGA score: 2 (mild) or 3 (moderate)

11 Pharmacokinetic Analyses

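### SAP 10.4 carries the Mantel-Haenszel risk-difference interval into small subgroups with no provision for sparse or zero-event tables, where its coverage can fall well below 95%

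*SAP*

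**What the plan says.** SAP 10.1.1 compares each OPA-15406 group with vehicle on IGA success. It gives a Cochran-Mantel-Haenszel p-value stratified by baseline IGA and, for the size of the difference, "a Mantel-Haenszel estimator of the common risk difference and its two-sided 95% confidence interval". The code line is "tables BaselineIGA*Treatment*Response/riskdiff(common) cmh", with no further interval option. An exact method appears only for each arm's own rate: "two-sided 95% confidence interval for the incidence of success in IGA in each treatment group will also be calculated using Clopper-Pearson method".

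SAP 10.4 then states: "Incidence of success in IGA will also be analyzed in the following subgroups in the same manner as described in" Section 10.1.1. The subgroups are age (below 7, or 7 and over), sex, and baseline IGA (mild or moderate). Their expected sizes are not given. The only related figure is the floor of 8 subjects aged 2 to 6 across all arms (Protocol 3.3.1).

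Protocol 7.4.2 calls the adjusted difference and its interval the primary analysis of IGA success, which is a secondary endpoint. SAP 6.6 says "No significance tests will be used in this trial; therefore, no significance levels are set" and keeps a two-sided 95% confidence coefficient.

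**The concern.** The expected vehicle rate is 2.7%, so zero responders on vehicle is the likeliest result even with the full arm: 0.973^20 = 0.578. In a single stratum, an arm with no responders adds nothing to an SE built from observed proportions. With no responder in either arm the SE is zero and the interval is [0, 0]. Printed in a subgroup table, that would look like certainty of no difference where almost nothing is known.

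The mild subgroup is the most exposed because of how success is defined. On the scale "0 = clear, 1 = almost clear, 2 = mild, 3 = moderate, 4 = severe/very severe", subjects must reach 0 or 1 "with an improvement by at least 2 grades from baseline are defined as responders". A subject starting at 2 must therefore reach 0, while a subject starting at 3 need only reach 1.

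What is at stake is how the subgroup differences are read. With no significance level set, the interval is the natural guide to their uncertainty.

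**Working it through.** **Inputs.** The success rates of 20.93%, 14.63% and 2.7%, and 20 subjects per arm, come from SAP 12.2. The 95% two-sided level comes from SAP 6.6. Subgroup sizes, and success rates by baseline IGA, are assumptions.

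**The plan's own figures.** Full enumeration of binomial tables at 20 per arm gives 95.5%, 86.9%, 71.5% and 58.9% for the four point-estimate probabilities in SAP 12.2. The plan states 96.2%, 88.3%, 71.5% and 60.6%. All agree within 2 points, so the rates and arm size are read correctly. These figures concern the ordering of point estimates and say nothing about interval coverage.

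**Interval.** The common difference is d = Σ w_k d_k / Σ w_k with w_k = n1k·n0k/N_k, and the limits are d ± 1.96 SE. With one stratum and n per arm, the Sato and Greenland-Robins variances both reduce to

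SE² = [p1(1 − p1) + p0(1 − p0)]/n, using observed proportions.

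Example: for 2/10 versus 0/10, SE = √(0.2 × 0.8/10) = 0.126, all of it from the active arm. The limits are −0.05 to 0.45.

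**Subgroups, one stratum, overall rates.** Each pair below is 1% versus vehicle, then 0.3% versus vehicle. The chance of [0, 0] is [(1 − p1)(1 − p0)]^n. At 10 per arm it is (0.7907 × 0.973)^10 = 0.073 and (0.8537 × 0.973)^10 = 0.156.

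| Assumed n per arm | Coverage | Chance of [0, 0] |
|---|---|---|
| 3 | 53.5%, 37.2% | 45.5%, 57.3% |
| 5 | 68.4%, 58.0% | 27.0%, 39.5% |
| 10 | 87.4%, 78.7% | 7.3%, 15.6% |
| 15 | 91.4%, 89.5% | 2.0%, 6.2% |
| 17 | 88.7%, 91.2% | 1.2%, 4.3% |

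At 10 per arm most misses are upper limits below the true difference: 9.6% and 20.6%, against a nominal 2.5%.

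**Mild subgroup.** Suppose the mild rate is half the moderate rate, strata are equal and overall rates are unchanged. The mild rates are then two thirds of the overall rates: 0.1395, 0.0975 and 0.018. At 10 per arm coverage is 77.1% and 68.7%, with [0, 0] in (0.8605 × 0.982)^10 = 18.6% and (0.9025 × 0.982)^10 = 29.9%.

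**Age or sex subgroup, 10 per arm stratified 5 mild/5 moderate.** With equal rates, coverage is 87.4% and 78.7% (Sato) or 86.7% and 77.2% (Greenland-Robins). If only moderate subjects respond, it is 92.4% and 82.1%, or 84.7% and 80.1%.

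**Main analysis, 20 per arm.**

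| Scenario (mild/moderate per arm) | Sato | Greenland-Robins |
|---|---|---|
| Equal rates, 10/10 | 91.4%, 93.1% | about 91%, 93% |
| Mild rate half, 10/10 | 91.8%, 93.3% | about 91%, 93% |
| Moderate-only response, 10/10 | 94.4%, 95.0% | 90.8%, 92.8% |
| Moderate-only response, 15/5 | 99.2%, 97.7% | 76.0%, 93.8% |

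**Score limits.** One-stratum Miettinen-Nurminen limits at 10 per arm cover 99.1% and 98.7%. For 0/n versus 0/n the limit d solves d/(1 − d) = 2 × 1.96²/(2n − 1). That gives ±0.29 at n = 10 and ±0.61 at n = 3, in place of [0, 0].

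**The case against.** The strongest reply concerns weight. The figure of 10 per arm is not in the documents, and larger subgroups do better. If the 2-to-6 group sits at its floor of 8, the older group has about (60 − 8)/3 ≈ 17 per arm, where coverage is near that of the main analysis. The variance formula is inferred, and what the procedure prints for a table with no responders is not documented. The same section also requires exact limits for each arm, so a reader of 0/10 versus 0/10 would see 0 to 31% for each arm beside any [0, 0]. The endpoint is secondary, without multiplicity adjustment or decision rule.

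Much of this stands, and it is why the priority is low. It does not remove the point. With 20 per arm, the two levels of a subgroup cannot both exceed 10 in any arm, so 10 is the most favourable size for the smaller level. With one stratum and equal arms the two variance formulas coincide, so the baseline-IGA subgroup figures do not depend on which is used. Clopper-Pearson limits describe each arm's own rate and do not repair the interval for the difference.

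A reader might go further and infer that the main interval is unsound and must be replaced. The documents do not support that. Coverage there depends on the variance formula and on success rates by baseline IGA, and neither is given. The 76.0% in the 15/5 case reflects that choice of formula in an extreme scenario. It is not evidence about the plan. Score limits over-cover in the main analysis (96.3% to 99.9%). Under the Sato variance they lie further from 95% than the planned limits in 8 of 10 scenario-by-dose comparisons, including three of the five for 1% versus vehicle.

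**Conclusion.** The point holds for the subgroups. SAP 10.4 reuses an interval that, read as estimate ± 1.96 SE, covers 87.4% and 78.7% at an assumed 10 per arm and can collapse to [0, 0]. Smaller subgroups fare much worse: 53.5% and 37.2% at 3 per arm, a size near the floor for ages 2 to 6 and not an expected count. At 15 per arm the shortfall is moderate (91.4% and 89.5%). Mild baseline IGA is the most exposed subgroup, by the definition of success.

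For the main analysis the shortfall is modest, about 91% and 93% with equal or half rates. Replacing that interval is optional.

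These sizes rest on assumed subgroup counts, on applying the plan's overall rates within subgroups except where stated, and on an inferred interval formula. The primary safety endpoint is not affected.

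**What to change.** Keep the Mantel-Haenszel point estimate and the CMH p-value throughout.

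Add to SAP 10.4:

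> Subgroup 95% limits for the difference will be Miettinen-Nurminen score limits. They will be unstratified in the baseline-IGA subgroups. In the age and sex subgroups they will be stratified by baseline IGA with Mantel-Haenszel weights. A stratum that is empty in one arm gets zero weight. If no stratum has subjects in both arms, the difference is reported as not estimable.

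In SAP 10.1.1, keep the planned main interval, name its variance formula, and add the stratified score limits as a supplementary interval. Change the code to match. The work is a few sentences and some programming before database lock.

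**Cost.** Subgroup limits become wider and conservative. At 10 per arm, mean width rises from 0.49 to 0.64 (1% versus vehicle) and from 0.41 to 0.63 (0.3% versus vehicle). Zero is excluded less often: 27.5% falls to 10.7%, and 13.2% to 3.5%. At 3 per arm the score limits average about 1.2 wide and say little, but they show that openly. In the main analysis with equal rates and 10/10 strata, the supplementary limits would average 0.43 against 0.37, and 0.41 against 0.32 (Sato).

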- 5) Change from baseline in VRS for pruritus up to Day 7 will be calculated. Using the OC and LOCF data sets up to Day 7, ANCOVA with factors of treatment (0.3% or 1% OPA-15406 groups, vehicle group), and baseline value will be applied to the change from baseline up to each timepoint based on OC and LOCF dataset. The least square mean of each treatment group will be calculated by timepoint. Also, the difference in the least square means between the vehicle group and each OPA-15406 group, and the two-sided 95% confidence interval and p-value will be calculated. Using the OC and LOCF data sets, the descriptive statistics will be calculated for measured values and changes from baseline by treatment group for each timepoint. The data will be collected at 4, 8, and 12 hours after the start of administration, 1 day after the start of administration (morning and night), and thereafter in the same manner up to Day 7 (morning).
- 6) For time to response in IGA and VRS for pruritus, Kaplan-Meier plots will be generated for each treatment group and vehicle group. For IGA, subjects with an IGA score is 0 (clear) or 1 (almost clear) with an improvement by at least 2 grades

from the baseline are defined as responders. For VRS for pruritus, subjects with VRS score of 0 (none) or 1 (mild) with an improvement by at least 1 grade from the baseline are defined as responders.

- 7) The descriptive statistics (number of subjects, arithmetic mean, standard deviation, coefficient of variation, minimum value, median value, and maximum value) of plasma OPA-15406 concentrations will be calculated by treatment group and by timepoint.
- 8) The descriptive statistics (number of subjects, arithmetic mean, standard deviation, coefficient of variation, minimum value, median value, and maximum value) of plasma OPA-15406 concentrations adjusted for affected area (%) per total BSA at baseline evaluation will be calculated by treatment group and by timepoint.
- 9) The descriptive statistics (number of subjects, arithmetic mean, standard deviation, coefficient of variation, minimum value, median value, and maximum value) of plasma OPA-15406 concentrations will be calculated by treatment group, by timepoint, and by affected area per total BSA at baseline examination (5% to <10%, ≥10% to <30%, and ≥30%).

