
10.1.2 Changes From Baseline in Overall EASI Score and EASI Symptom Scores

Based on the OC data set, the change from baseline in EASI score (at Week 1, Week 2, and Week 4; if the timing of discontinuation falls within the allowable window of a timepoint, the data at discontinuation will be included as the data for the timepoint) will be analyzed using the MMRM analysis with treatment (0.3% or 1% OPA-15406 group, and vehicle group), timepoint, and interaction between treatment and timepoint as factors and baseline EASI score as a covariate. An unstructured covariance matrix will be used to model the within-subject errors and Kenward-Roger method will be used to calculate the standard error of fixed-effects and the degree of freedom. If the MMRM procedure fails to converge under unstructured covariance structure, the following structure will be used in the order of 1) heterogeneous toeplitz, 2) heterogeneous autoregressive of order 1, 3) heterogeneous compound symmetry and the first (co)variance structure converging to the best fit will be used.

The least square mean of each treatment group will be calculated by timepoint. For overall EASI score, the least square mean and the standard error will be plotted by timepoint for each treatment group. The difference in the least square mean between the vehicle group and each OPA-15406 group, and the two-sided 95% confidence interval and p-value will be calculated at Week 1, Week 2, and Week 4.

Based on the OC and LOCF data sets, ANCOVA model with treatment (0.3% or 1% OPA-15406 group, and vehicle group) as a factor and baseline EASI score as a covariate will be applied to the change from baseline up to each timepoint. The least square mean in each treatment group will be calculated by timepoint. The difference in the least square

mean between the vehicle group and each OPA-15406 group, and the two-sided 95% confidence interval and p-value will be calculated at Week 1, Week 2, and Week 4. Based on the OC and LOCF data sets, measured values and changes from baseline in IGA at Week 1, Week 2, and Week 4 will be summarized by treatment group using descriptive statistics. For the overall EASI score, the mean with standard error of measured values (in the OC and LOCF data sets) will be plotted by timepoint for each treatment group.

EASI scores for body regions (face, neck, and head; upper limbs; trunk; and lower limbs) will be analyzed in the same manner as the overall EASI score.

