10.1.3 Change From Baseline in Visual Analogue Scale for Pruritus

The change from baseline in visual analogue scale (VAS) for pruritus will be analyzed in the same manner as that in the overall EASI score or each EASI symptom score.

10.1.4 Change From Baseline in VRS for Pruritus up to Day 7

The change from baseline in VRS score for pruritus up to Day 7 will be analyzed in the same manner as that in overall EASI score or each EASI symptom score. Data will be collected at baseline, 4, 8, and 12 hours after the start of administration, 1 day after the start of administration (morning and night), and thereafter in the same manner up to Day 7 (morning). The same analysis will be performed by the time zone of assessment (morning or evening). Morning or evening will be determined based on the time label entered in the case report form (CRF), not using the timepoints defined in Table 6.4-2, except the baseline, which is irrespective of the time zone of assessment. Data will be collected at baseline, and the timepoints specified above on Day 1 to Day 7.

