12.2 Rationale for the Number of Subjects

The sample size of 20 subjects for each group, a total of 60 subjects, has been established in consideration of the feasibility of the trial and the number of subjects needed to evaluate efficacy and safety. Assuming that the probabilities of success in IGA for each group are the same as those in the phase 2 trial outside Japan (271-12-205), the expected incidence of success in the 1% OPA-15406 group, the 0.3% OPA-15406 group, and the vehicle group is 20.93%, 14.63%, and 2.7%, respectively. In that case, the probability of the 1% group > the vehicle group, the 0.3% group > the vehicle group, and the 1% group minus the vehicle group > 10% in the point estimate of incidence of success is 96.2%, 88.3%, and 71.5%, respectively. Also, the probability of the 1% group > the 0.3% group \geq the vehicle group in point estimate of incidence of success is 60.6%.

13 Changes From Analysis Planned in the Protocol

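### The MMRM fallback code in SAP 10.1.1 replaces the stated Kenward-Roger method with an uncorrected sandwich, so its nominal 95% intervals would cover about 93%

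*SAP*

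**What the plan says.** - **Prose.** SAP 10.1.1 (IGA) specifies an unstructured MMRM with Kenward-Roger. SAP 10.1.2 (EASI) repeats it: "Kenward-Roger method will be used to calculate the standard error of fixed-effects and the degree of freedom". If the fit does not converge, heterogeneous Toeplitz, heterogeneous AR(1) and heterogeneous compound symmetry are tried in turn. Nothing is said about changing the standard error or the degrees of freedom.
- **Code.** The main code block in SAP 10.1.1 has the option ddfm = kr. The fallback block begins "proc mixed method = reml empirical", and its model statement has no ddfm option.
- **Reach.** The code is printed once, for IGA. SAP 10.1.3 to 10.1.6 refer VAS, VRS, POEM and affected BSA back to the EASI method. For VRS, SAP 10.1.4 says: "The change from baseline in VRS score for pruritus up to Day 7 will be analyzed in the same manner". Table 6.4-2 defines 16 VRS timepoints. Reuse of the fallback code for these endpoints is a fair inference, not an explicit statement.
- **VRS in the protocol.** Section 7.4.2 item 5 gives ANCOVA: "Using the OC and LOCF data sets up to Day 7, ANCOVA with factors of treatment". The synopsis instead applies the IGA method to all other secondary endpoints and singles out VRS only for its Day 7 horizon.
- **Role of the intervals.** SAP 6.6 says "No significance tests will be used in this trial; therefore, no significance levels are set", and sets two-sided 95% confidence intervals.

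**The concern.** A programmer cannot follow both the prose and the code once the unstructured fit has failed. The choice is not cosmetic. The classical sandwich is biased downward with few subjects. Without a ddfm option the software default applies, which here is likely to be well above the number of children. Both errors narrow the interval. With no significance level set, the 95% intervals are how these secondary endpoints will be read, so an interval that is too narrow overstates what arms of 20 or fewer can show about dose response.

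**Working it through.** **1. The plan's own figures.** SAP 12.2 gives "The sample size of 20 subjects for each group, a total of 60 subjects", with assumed success rates for 1%, 0.3% and vehicle of "is 20.93%, 14.63%, and 2.7%, respectively". Exact enumeration of independent binomials with n = 20 gives 95.5%, 86.9%, 71.5% and 58.9%, against the stated 96.2%, 88.3%, 71.5% and 60.6%. The differences are 0.7, 1.4, 0.0 and 1.7 points. This supports 20 per arm as the planning size. The documents give no figure for the coverage of an MMRM interval.

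**2. Inputs.**
- From the documents: three arms, 60 children, three visits (IGA, EASI, VAS, POEM, BSA) or 16 timepoints (VRS). VAS and VRS are for ages 7 to 14 only. At least 8 children are aged 2 to 6 (Protocol 3.3.1), so VAS and VRS have at most 60 − 8 = 52 children, about 17 per arm.
- Assumed: variances, correlations and missing rates; between-within as the default degrees of freedom; and 13 per arm as a low case (39 children aged 7 to 14), which appears nowhere in the documents.

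**3. Degrees of freedom.** With T timepoints, N children and p = 3T + 1 fixed effects, the within-subject default is N·T − p − (N − 4). At N = 60:
- T = 3: 180 − 10 − 56 = 114.
- T = 16: 960 − 49 − 56 = 855.

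The between-subject figure is N − 4 = 56.

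**4. Coverage of the fallback.** I simulated with no treatment effect and complete data, and took the last-timepoint contrast. With working weight W, A = ΣXᵢ′WXᵢ and uᵢ = Xᵢ′Wrᵢ (rᵢ the residuals), the sandwich variance is A⁻¹(Σuᵢuᵢ′)A⁻¹. There were 20,000 runs for T = 3 and 5,000 for T = 16, the latter with a misspecified AR(1) working matrix. The working matrix was held fixed. Width is relative to an exact t interval on N − 4 degrees of freedom.

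| Timepoints | Per arm | Coverage | SE / true SD | Relative width |
|---|---|---|---|---|
| 3 | 20 | 93.6% | 0.962 | 0.945 |
| 3 | 17 | 93.6% | 0.967 | 0.947 |
| 3 | 13 | 92.7% | 0.944 | 0.917 |
| 16 | 20 | 93.3% | 0.960 | 0.934 |
| 16 | 17 | 92.9% | 0.959 | 0.929 |
| 16 | 13 | 92.3% | 0.955 | 0.915 |

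The 16-timepoint row at 20 per arm is for comparison only, since VRS cannot reach that size. Replacing the default degrees of freedom by N − 4 raises coverage only to 93.9% (T = 3) and 93.8% (T = 16) at 20 per arm. Most of the shortfall therefore comes from the sandwich itself.

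**5. Check with re-estimated covariance.** Refitting heterogeneous Toeplitz by REML at 20 per arm with three visits (1,500 runs, Monte Carlo error about 0.6 points) gave 93.5% for the sandwich. The model-based standard error with N − 4 degrees of freedom, standing in for Kenward-Roger, gave 95.2%. The sandwich interval was 0.95 times as wide.

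**6. Would the fallback be used?** An unstructured matrix has T(T + 1)/2 parameters: 3 × 4/2 = 6 for three visits and 16 × 17/2 = 136 for VRS. I fitted the 16-timepoint model by my own REML scoring routine (50-iteration limit) to simulated 0–3 scores. The table gives fits that converged.

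| Missing at Hours 8 and 12 / elsewhere | 17 per arm | 13 per arm |
|---|---|---|
| none | 60/60 | 60/60 |
| 5% / 2% | 40/40 | 39/40 |
| 15% / 3% | 40/40 | 21/40 |
| 30% / 5% | 19/60 | 0/60 |
| 50% / 5% | 0/60 | 0/60 |

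The documents give no missing-data rate. They do make the 8-hour and 12-hour assessments optional (Protocol 3.7.1.5), and they end the diary on the morning of a Week 1 visit that may fall two days early (Protocol 3.7.1.6).

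**The case against.** **A sandwich can be deliberate.** Pairing it with a structured covariance guards against choosing the wrong structure, and the code is printed in advance. That stands as a reason for using a sandwich. It does not explain why the prose still promises Kenward-Roger, or why no small-sample correction is specified.

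**The stakes are limited.** This also stands. The primary endpoint is adverse events, and the main IGA success analysis is a Cochran-Mantel-Haenszel risk difference. IGA, EASI, VAS, VRS, POEM and BSA all have parallel ANCOVA tables that never use this code.

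**VRS and failure to converge.** From 136 parameters and at most 52 children, a reader might infer that the VRS model will probably fail. The documents do not support that: with complete or nearly complete diaries it converged at 17 per arm in every run, and failure became common there only under heavier missingness that I had to assume.

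**VRS and ANCOVA.** From Protocol 7.4.2 item 5, a reader might infer that the SAP silently replaced ANCOVA by MMRM. It did not. The synopsis already extends the IGA method to the other secondary endpoints, and ANCOVA for VRS remains planned (CT-5.7.2 and CT-5.7.3). What remains is an inconsistency within the protocol.

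**Morning and evening tables.** The 136-parameter argument does not carry over to CT-5.7.4, where the split roughly halves the timepoints; with eight, for example, there are 8 × 9/2 = 36 parameters.

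**Conclusion.** The point holds: the fallback code contradicts the stated standard-error method. If it is used, nominal 95% intervals cover about 93% (roughly 92% to 94%), so the error rate is about 6% to 8% instead of 5%, and the intervals are about 5% to 9% too narrow. An error rate near 10% might be inferred, but it needs half of the Hour 8 and Hour 12 assessments to be missing, which the documents do not indicate.

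The effect is modest, runs in one direction, and is confined to secondary estimates without multiplicity adjustment. Six covariance parameters give no reason to expect failure for the three-visit endpoints. For the 16-timepoint VRS model failure is plausible if diaries are incomplete, but its probability cannot be derived from the documents.

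The size rests on the assumed covariances, default degrees of freedom and complete data. The lower end of coverage uses 13 per arm, which is an assumption. My fitting routine is not PROC MIXED, so the convergence counts are indicative only.

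**What to change.** Before the SAP is finalised:

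- **Fallback code.** Remove the empirical option and keep ddfm = kr with TOEPH, ARH(1) or CSH. If a sandwich is wanted, specify a small-sample-corrected one with suitable degrees of freedom.
- **Prose.** State in SAP 10.1.1 and 10.1.2 the standard-error and degrees-of-freedom method for the fallback, and that the same code serves VAS, VRS, POEM and BSA.
- **VRS.** Name the planned ANCOVA (CT-5.7.2, CT-5.7.3) as the main analysis, or prespecify a structured covariance with Kenward-Roger for CT-5.7.1. Record in the SAP how the protocol synopsis and Protocol 7.4.2 item 5 are reconciled. CT-5.7.1 and CT-5.7.4 need not be deleted.

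The cost is two code options and a few sentences. The downside is that model-based standard errors rely on the chosen covariance structure, which is a reason to keep the heterogeneous structures.
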